### **3.8 Schedule of Events**

Table 1 below describes the daily schedule of events from Screening Visit 1 through End-of-Study Visit 9.

**Table 1: Daily Schedule of Events from Screening Visit 1 through End-of-Study Visit 9**

Assessments	Screening	Placebo	Treatment						Unscheduled Visit	End-of-Study/ Early Termination
			0	1	2	4	8	12		
Week	up to -6	-2	0	1	2	4	8	12	Not Defined	16
Days	Up to -42	-14	0±4	7±4	14±4	28±4	56±4	84±4		112±4
Visit	1	2	3	4	5	6	7	8	Unscheduled	9
Written informed consent	X									
Inclusion/Exclusion	X									
Medical and social history (including tobacco, alcohol, caffeine, and drug use)	X									
Prior and Concomitant Medication 	X	X	X	X	X	X	X	X		X
Demographics (sex, age, race and ethnicity)	X									
Complete physical examination	X		X					X		(X  )
Height, Weight and BMI 	X	X	X	X	X	X	X	X		X
Pregnancy Test 	X	X	X							
Treatment Administration 		X 	X 	X	X	X 	X 			
Dispense/Collect Medication 		X	X	X	X	X	X	X		X
Medication compliance check			X	X	X	X	X	X		
ECG	X									(X  )

Assessments	Screening	Placebo	Treatment						Unscheduled Visit	End-of-Study/ Early Termination
			0	1	2	4	8	12		
Week	up to -6	-2	0	1	2	4	8	12	Not Defined	16
Days	Up to -42	-14	0±4	7±4	14±4	28±4	56±4	84±4		112±4
Visit	1	2	3	4	5	6	7	8	Unscheduled	9
Vital signs 	X	X	X	X	X	X	X	X		(X  )
Clinical laboratory evaluations 	X		X			X	X	X	(X  )	X
Fasting blood glucose and fasting Insulin 		X	X			X	X	X	(X  )	X
Self-monitored fasting morning blood glucose 		X	X	X	X	X	X	X		
Dispense Diary/ Review Diary Data		X	X	X	X	X	X	X		X
Adiponectin Test			X			X	X	X		X
HbA1c	X							X		X
Blood lipids: Total cholesterol, LDL, HDL, Triglycerides	X		X			X	X	X		X
CAP-Fibroscan	X		X					X		
MRI-PDFP	X							X		
Viral serology 	X									
TSH and FSH 	X									
AE/SAE assessment 	X	X	X	X	X	X	X	X	X	X

## Table 1 Footnotes

-  Prior and concomitant medications will be reviewed at Screening. Concomitant medications will be reviewed through Visits 2-9.
-  Only if investigator deems necessary.
-  Height measurement and BMI calculation will be performed at Screening only. Weight will be measured as indicated.
-  Serum pregnancy test will be performed at Screening (Visit 1). Urine pregnancy test will be performed at Visit 2 and Visit 3.
-  Blood samples taken prior to dosing in clinic and snack provided after 30-45 minutes at Visit 2, 3, 6, and 7.
-  Study medication will be dispensed and collected at Visits 2-8 and collected at End-of-Study/Early Termination Visit.
-  Vital signs (blood pressure, heart rate, oral temperature). Vital signs will be measured in the sitting position after at least 5 minutes of rest.
-  Serum Chemistry: Sodium, Potassium, Glucose, BUN, Creatinine, BUN/Creatinine, Chloride, Calcium, Protein, Albumin, Globulin (total), A/G Ratio, SGOT (AST), SGPT (ALT), Bilirubin (total), Alkaline Phosphatase, CO2, Creatine Phosphokinase (CPK), Total cholesterol, LDL, HDL, Triglycerides, Thyroid Stimulating Hormone (TSH, screening only). Hematology: Hemoglobin, Hematocrit, RBC, WBC (total count and differential count), Platelets Count, Mean Platelet Volume (MPV), MCV, MCH, MCHC, RDW, Neutrophils (absolute value and %), Bands (ABS CNT), Bands, Lymphocytes (absolute value and %), Monocytes (absolute value and %), Eosinophils (absolute value and %), Basophils (absolute value and %), RBC Morphology. Urinalysis is not performed in this study.
-  Fasting blood glucose and insulin will be used to determine Homeostasis Model Assessment (HOMA) estimates. During an Unscheduled Visit only fasting blood glucose will be collected, if investigator deems necessary.
-  Self-monitoring (finger-stick) of fasting blood glucose will be required 3 days weekly in the morning, before breakfast, and recorded in patient diaries.
-  HCV-Ab (hepatitis C virus antibody), HBsAg (surface antigen of the hepatitis B virus), HBcore-total (total hepatitis B core antibody), HBs Ab (hepatitis B surface antibody), anti-HIV Ab (human immunodeficiency virus antibody).
-  Screening labs will include standard hematology, fasting serum chemistry, plus TSH. FSH will also be performed for women who are post-menopausal, if results are not available.
-  Adverse events will be collected throughout the study beginning from the time the patient signs the consent form until the EOS (Visit 9) evaluations.

## 4 STUDY SUBJECT SELECTION

### 4.1 Inclusion Criteria

Each subject must meet all of the following criteria to be eligible for the study:

#### Inclusion Criteria

1. Male or female aged 18-70 years.
2. BMI  $\geq 25$ .
3. Known type 2 DM according to American Diabetic Association (one of the three needed): Fasting Plasma Glucose  $\geq 126$  mg/dl or 2h postprandial (PG) following 75g OGTT  $\geq 200$  mg/dl or HbA1c  $> 6.5\%$  or on treatment with metformin only or metformin in addition to no more than two of the following medications sulfonylurea, DPP-4 inhibitors, GLP-1 receptor agonists, Thiazolidinediones (TZDs).
4. Diagnosis of NAFLD by non-invasive determination of hepatic steatosis grade S1, defined as hepatic steatosis  $> 8\%$ , by MRI- PDFF and CAP FibroScan  $\geq 238$  dB/m.
5. Liver enzyme abnormalities: ULN  $\leq 5$  times.
6. Fibrosis score  $1 \leq F \leq 3$  as defined by FibroScan measurement (Liver stiffness measurement, LSM) of  $6 \leq \text{LSM} \leq 12$  kPa.
7. Signature of the written informed consent.
8. Negative serum pregnancy test at study entry for females of childbearing potential.
9. Women of childbearing potential must have a negative urine pregnancy test result prior to the start of the run-in period and initiation if active dosing. Males and females of childbearing potential must use two methods of contraception (double barrier method), one of which must be an acceptable barrier method from the time of screening to the last study visit (22 weeks). Barrier methods of contraception include male condoms plus spermicide, diaphragm with spermicide plus male condom, and cervical cap with spermicide plus male condom. Acceptable methods of birth control include abstinence, oral contraceptives, surgical sterilization, vasectomy, the contraceptive patch, and the contraceptive ring. If a subject is not usually sexually active but becomes active, he or his partner should use medically accepted forms of contraception. Sperm donations will not be allowed for the duration of the study and for 90 days after the last dose of study drug.  
Females of non-childbearing potential are defined as postmenopausal who a) had more than 24 months since last menstrual cycle with menopausal levels of FSH (FSH Level  $> 40$ ), b) who are surgically menopausal (surgical sterility defined by tubal occlusion, bilateral oophorectomy, bilateral salpingectomy or hysterectomy).
10. For hypertensive patients, hypertension must be controlled by stable dose of anti-hypertensive medication for at least 2 months prior to screening (and the stable dose can be maintained throughout the study) with BP  $< 150/ < 95$  mmHg.
11. Patients previously treated with vitamin E ( $> 400$  IU/day), Polyunsaturated fatty acid ( $> 2$  g/day) or Ursodeoxycholic acid fish oil can be included if drugs are stopped at least 3 months prior to enrolment and up to the end of the study.
12. Glycaemia must be controlled (Glycosylated Hemoglobin A1c  $\leq 8.5\%$ ) while any HbA1c increment should not exceed 1% during 6 months prior to enrolment).

## 4.2 Exclusion Criteria

Subjects who meet any of the following criteria must be excluded from the study:

1. Patients with active (acute or chronic) liver disease other than NASH (e.g. viral hepatitis, genetic hemochromatosis, Wilson disease, alpha-1 antitrypsin deficiency, alcohol liver disease, drug induced liver disease) at the time of enrolment.
2. ALT or AST > 5 times ULN.
3. Abnormal synthetic liver function (serum albumin  $\leq$ 3.5gm%, INR >1.3).
4. Known alcohol and/or any other drug abuse or dependence in the last five years.
5. Weight >120 Kg (264.6 lbs.).
6. Known history or presence of clinically significant, cardiovascular, gastrointestinal, metabolic (other than diabetes mellitus), neurologic, pulmonary, endocrine, psychiatric, neoplastic disorder or nephrotic syndrome.
7. History or presence of any disease or condition known to interfere with the absorption, distribution, metabolism or excretion of drugs including bile salt metabolites (e.g. inflammatory bowel disease (IBD), previous intestinal (ileal or colonic) operation, chronic pancreatitis, celiac disease or previous vagotomy.
8. Weight loss of more than 5% within 6 months prior to enrolment.
9. History of bariatric surgery.
10. Uncontrolled blood pressure BP  $\geq$ 150/ $\geq$ 95.
11. Non type 2 DM (type 1, endocrinopathy, genetic syndromes etc.).
12. Patients with HIV.
13. Daily alcohol intake >20 g/day (2 units/day) for women and >30 g/day (3 units/day) for men.
14. Treatment with anti-diabetic medications other than metformin and more than-two of the following medications sulfonylurea, DPP-4 inhibitors, GLP-1 receptor agonists, TZDs
15. Metformin, fibrates, statins, not provided on a stable dose in the last 6 months.
16. Patients who are treated with valproic acid, Tamoxifen, methotrexate, amiodarone.
17. Chronic treatment with antibiotics (e.g. Rifaximin).
18. Homeopathic and/or Alternative treatments. Any treatment must be stopped before the screening period.
19. Uncontrolled hypothyroidism defined as Thyroid Stimulating Hormone >2X the upper limit of normal (ULN). Thyroid dysfunction controlled for at least 6 months prior to screening is permitted.
20. Patients with renal dysfunction: eGFR < 40 ml/min.
21. Unexplained serum creatinine phosphokinase (CPK) >3X the upper limit of normal (ULN). Patients with a reason for CPK elevation may have the measurement repeated prior to enrolment; a CPK retest > 3X ULN leads to exclusion.
22. Subjects meeting criteria for contraindication for MRI – including the following:
  - History of severe claustrophobia impacting ability to perform MRI during the study, even despite mild sedation/treatment with an anxiolytic.
  - Subjects with metal implants, devices, paramagnetic objects contained within the body and excessive or metal containing tattoos.
  - Subjects unable to lie still within the environment of the MRI scanner or maintain a breath hold for the required period to acquire images, even despite mild sedation/treatment with an anxiolytic.

23. Subject participated in a clinical research study involving a new chemical entity within 4 weeks of study entry.
24. Known allergy to soy.

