Despite the high prevalence of NAFLD, no safe and effective treatment is currently available. Management strategies for NAFLD/NASH rely primarily on non-pharmacologic measures. Since patients with NAFLD without steatohepatitis have excellent prognoses from a liver standpoint, treatments aimed at improving liver disease should be limited to those with NASH.

Life-style modifications are effective but adherence is difficult to maintain. Bariatric surgery can be performed in selective obese patients, but is too drastic to be the treatment of choice and thus it is not recommended for treating NASH. Vitamin E has been effective in treating nondiabetic NASH patients without cirrhosis. The long-term safety and efficacy of pioglitazone are not clear in NASH. Metformin, ursodeoxycholic acid, omega 3 fatty acids, and statins are not considered as therapy for NAFLD/NASH patients.

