### 4.3 Subject and Trial Discontinuation

Subjects may choose to withdraw from this study at any time for any reason without penalty of jeopardizing their health care or loss of benefits to which the subject is otherwise entitled.

Within the provisions of informed consent and good clinical judgment with respect to safety, every attempt will be made to have subjects complete the study. The following are reasons to terminate a subject's participation in the study:

1. Subject experiences an AE that in the judgement of the Investigator poses a significant risk to the subject for continued participation in the study.
2. Subject uses any medication that in the judgment of the Investigator poses a significant risk to the subject for continued participation in the study or that will interfere with the interpretation of the results of the study.
3. Subject becomes pregnant.
4. Significant protocol violation or noncompliance on the part of the subject or the Investigator.
5. Intercurrent illness that requires treatment that is not consistent with the protocol requirements, or intercurrent illness or the associated treatment that in the judgment of the Investigator poses a significant risk to the subject for continued participation in the study.
6. Subject wishes to withdraw for any reason.
7. Sponsor elects to end the study, or the Investigational Site elects to end the study at their site.
8. Any other reason that in the judgment of the Investigator poses unacceptable risk to the subject.

Subjects who withdraw from the study prior to treatment may be replaced. Subjects who are withdrawn and have received at least one treatment will not be replaced. Subjects who discontinue study drug treatment will not be replaced.

Except in cases of emergency, the Investigator should consult with the Sponsor and the Medical Monitor before removing the subject from the study. In some circumstances it may be necessary to temporarily interrupt treatment as a result of AEs that may have an unclear relationship to the IMP. The Investigator should obtain approval from the Sponsor and Medical Monitor before restarting IMPs that were temporarily discontinued for an AE.

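### Exclusion 15 asks for a 6-month stable dose of metformin, fibrates and statins but not of the four add-on glucose-lowering classes that inclusion 3 permits: a minor gap that is cheap to close

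*Combined protocol and SAP*

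**What the plan says.** The stable-dose rule is exclusion 15 in Section 4.2, repeated in the Synopsis: "Metformin, fibrates, statins, not provided on a stable dose in the last 6 months". It names three drug groups.

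Inclusion 3 (Section 4.1) allows metformin alone or with up to two from "sulfonylurea, DPP-4 inhibitors, GLP-1 receptor agonists, Thiazolidinediones (TZDs"). It sets no minimum duration and no dose condition. Exclusion 14 limits which agents may be used and how many, not how long they have been taken.

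Other entry rules bear on the point indirectly:

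- Inclusion 12 caps HbA1c at 8.5% and adds "while any HbA1c increment should not exceed 1% during 6 months prior to enrolment".
- Exclusion 8 removes patients with "Weight loss of more than 5% within 6 months prior to enrolment".
- Inclusion 10 asks for 2 months of stable antihypertensive dosing.
- Under inclusion 11, patients who took vitamin E, polyunsaturated fatty acids or ursodeoxycholic acid "can be included if drugs are stopped at least 3 months prior to enrolment and up to the end of the study".

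During the study, Section 5.7 has concomitant medication judged case by case, with Sponsor and Medical Monitor contact. Section 6.6 limits it to what is medically necessary and has dose increases noted. Section 4.3 item 2 allows removal of a subject using a drug "that will interfere with the interpretation of the results of the study". No section asks that add-on doses be held constant.

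MRI-PDFF is scheduled at Screening (up to Day -42) and Week 12 only (Table 1). Section 8.3.1 analyses liver fat by ANCOVA with treatment, country, site and the baseline value.

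**The concern.** The criteria treat similar situations differently. A patient whose metformin dose changed five months ago is excluded. A patient who started a GLP-1 receptor agonist or a thiazolidinedione last week can be eligible.

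If the new drug alters liver fat, much of its action could fall after the Screening scan and before the Week 12 scan. The baseline covariate cannot adjust for a change that comes after baseline is measured. The placebo run-in does not help either, because it follows the Screening scan and no second pre-treatment MRI-PDFF is taken.

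At stake is the precision of the MRI-PDFF contrast. MRI-PDFF is the only efficacy endpoint the protocol names (Sections 2.4 and 6.3), and the placebo arm would have about 10 completers.

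**Working it through.** **Inputs from the documents.** Up to 36 patients are randomized 2:1 to yield about 30 completers (Sections 5.2 and 8.1). That is 20 active and 10 placebo if losses are proportional. There are five sites. Section 8.1 states no SD, effect size or power, so the plan has no figure of its own to reproduce here.

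**Assumptions, not in the documents.** Residual SD of the MRI-PDFF outcome: 4 to 6 points. Completers who recently started an add-on: 2 to 6 of 30. Shift in liver fat between scans caused by the add-on: 3 points, with 0 and 8 as extremes.

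**Step 1: time between scans.** Nominally 42 + 84 = 126 days at most.

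**Step 2: standard error without starters.** SE = SD × sqrt(1/20 + 1/10) = 0.387 × SD, so 1.55 points at SD 4 and 2.32 at SD 6.

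**Step 3: variance added by starters.** If a share p has a shift of d points, the added variance is d² × p(1 − p). The SE ratio is sqrt((SD² + added variance)/SD²). For d = 3:

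| Starters of 30 | Added variance | SE rise, SD 4 | SE rise, SD 6 |
|---|---|---|---|
| 2 | 0.56 | 1.7% | 0.8% |
| 3 | 0.81 | 2.5% | 1.1% |
| 4 | 1.04 | 3.2% | 1.4% |
| 5 | 1.25 | 3.8% | 1.7% |
| 6 | 1.44 | 4.4% | 2.0% |

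For example, 4 starters at SD 4: 9 × (4/30) × (26/30) = 1.04, and sqrt(17.04/16) = 1.032.

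**Step 4: interval width.** Residual degrees of freedom are 30 − 1 (intercept) − 1 (treatment) − 4 (sites, with country nested) − 1 (baseline) = 23, so t = 2.069. Site imbalance is ignored. With 4 starters and a 3-point shift, the 95% half-width goes from 3.20 to 3.31 points at SD 4 and from 4.81 to 4.88 at SD 6.

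**Step 5: extremes.** With d = 0 nothing changes. With d = 8, which equals the liver-fat entry threshold of 8%, the SE rise is 5.4% (2 starters, SD 6) to 28.1% (6 starters, SD 4).

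**Step 6: do other rules close the gap?** Inclusion 12 limits a rise in HbA1c, so a fall after a new add-on passes. Exclusion 8 lets through weight loss of 5% or less. Sections 4.3 and 5.7 can reach a drug begun before Screening and continued, because Section 6.6 counts drugs taken after Visit 1 as concomitant. They work by judgement, though, and set no criterion for drugs that inclusion 3 expressly permits.

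**The case against.** The strongest objection is that the harm is conditional on something the documents never state. Nowhere do they say that any of the four classes changes liver fat. The nearest statement is "The long-term safety and efficacy of pioglitazone are not clear in NASH", which concerns one thiazolidinedione and says nothing about a 12-week imaging shift. This stands: a reader might infer that the gap certainly adds variance, and the documents do not support that.

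The size is also small. At a 3-point shift with 4 starters the half-width grows by about 0.1 point or less, on an interval already 3 to 5 points either side. Larger rises need an extreme shift. MRI-PDFF is secondary in an exploratory safety study that Section 8.1 describes as unpowered. All of this stands and sets the severity.

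Four stronger readings are tempting and should be resisted:

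- **Bias.** Changes made before randomization are independent of the assigned arm, so no systematic difference is expected from them.
- **Chance imbalance as a second harm.** The arms' starter shares would differ by 20 points or more with probability 0.10, 0.03, 0.27, 0.30 and 0.14 for 2 to 6 starters (hypergeometric, 30 completers, 10 on placebo). This is the same variance seen another way. For 4 starters at 3 points, the root-mean-square imbalance gives 0.134 × 3 = 0.40 point, against sqrt(1.04 × 0.15) = 0.395 from Step 3.
- **No safeguard at all.** The discretionary and indirect controls in Step 6 do reach some of these patients.
- **Self-contradiction.** The Introduction says that metformin and "ursodeoxycholic acid, omega 3 fatty acids, and statins are not considered as therapy for NAFLD/NASH patients", yet metformin, statins, fatty acids and ursodeoxycholic acid all have an entry rule while pioglitazone's class has none. But inclusion 11 also stops vitamin E, which the Introduction calls effective in nondiabetic NASH. The criteria are uneven; they do not contradict each other.

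**Conclusion.** The omission is verified, and no other section sets a pre-entry stability rule for the four classes. Its effect, if there is one, is lost precision on a secondary endpoint: an SE rise of about 1% to 4% for 2 to 6 recent starters, a 3-point shift and an SD of 4 to 6. All three inputs are assumed, and the rise is nil if the drugs leave liver fat unchanged. The planned primary safety evaluation is not affected. This is a minor point. It is worth acting on because the protocol already uses this kind of rule and extending it costs little.

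**What to change.** Reword exclusion 15, in Section 4.2 and the Synopsis, so that the 6-month stable-dose condition covers every glucose-lowering class permitted by inclusion 3, alongside fibrates and statins. If 6 months threatens recruitment, 3 months is a reasonable fallback and matches the interval in inclusion 11. Add one sentence, for instance in Section 5.7, asking that these doses be held stable through Visit 8 except where safety or rescue requires a change. The ANCOVA needs no change.

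Sites must check a longer dose history for these classes. Section 6.6 records medications only from 30 days before Visit 1, but exclusion 15 already needs a 6-month history for metformin. There may also be a few more screen failures. The documents give no basis for a number, and Section 4.3 lists slow recruitment among the possible reasons for stopping, hence the 3-month option.

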### **Proposed Mechanism**

Any attempt to develop an oral insulin modality must take into account two major obstacles that result from insulin's biochemical characteristics as a polypeptide: 1) Its direct transfer across the mucosal barrier is restricted; 2) it is subject to degradation by the proteolytic enzymes located in the stomach and intestinal lumen.

[figure not shown]
To overcome these barriers, Oramed has proposed a mechanism to prevent the digestion of the introduced hormone in the gastrointestinal tract and to facilitate its physiological absorption. After performance of a range of studies for optimization of co-factors to prevent the digestion of insulin, Oramed has identified the most efficacious formulation of encapsulated oral insulin. The proposed composition contains: (1) crystalline insulin, (2) EDTA as enhancer, (3) soybean trypsin (SBTI), and (4) omega 3-rich fish oil, in a coated capsule. These components are expanded upon in greater detail below. Each has a target function, which promotes the goals of our treatment modality. The chelating agent EDTA functions as an effective enhancer of the mixture. The SBTI prevents enzymatic degradation of the insulin by mucosal enzymes.

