### 3 INVESTIGATIONAL PLAN

#### 3.1 Overall Study Design and Plan

This is a double-blind, randomized, placebo-controlled, multi-center study using the oral ORMD-0801 insulin formulation in patients with NASH and confirmed type 2 DM. This exploratory multi-center study will enroll patients with NASH and type 2 DM between the ages of 18 and 70. Subjects will undergo a Screening Phase up to 42 days prior to the Treatment Phase, a Placebo Run-in Phase for 2 weeks, a Treatment Phase for 12 weeks and an End-of-Study Phase 4 weeks after completion of the Treatment Phase. Approximately 36 subjects will be randomized in a 2:1 ratio to receive either 8 mg ORMD-0801, 1 capsule twice a day (once in the morning approximately 30 to 45 minutes prior to breakfast and no later than 10 AM, and once at night between 8 PM to Midnight and no sooner than 1 hour after dinner) or matching placebo.

At Screening (Visit 1, up to week -6), subjects will sign the ICF and inclusion and exclusion criteria will be reviewed. Medical history, demographics (sex, age, race and ethnicity), and prior and concomitant medications will be recorded. Height and weight will be measured, and BMI will be calculated. Vital signs (SBP/DBP, heart rate and oral temperature), complete physical examination, 12-Lead ECG, clinical laboratory evaluations, serum pregnancy test for females of childbearing potential, blood lipids test, HbA1c, viral serology, CAP-Fibroscan and MRI-PDFF will be performed. For females of non-childbearing potential, FSH levels will be tested if results are not available. Adverse events will be monitored and recorded.

After Screening, each subject will undergo a Placebo Run-in Phase (Visit 2, to Week -2). Concomitant medications will be reviewed. All subjects will receive the morning treatment (Run-in Placebo) in clinic, 1 bottle of placebo medication and subject diaries will be dispensed. Vital signs (SBP/DBP, heart rate and oral temperature) and weight will be collected. Fasting blood glucose and fasting insulin will be measured, urine pregnancy test will be performed for females of childbearing potential. Self-monitored fasting morning blood glucose (finger-stick) will be recorded in the patient diaries 3 days weekly in the morning. Adverse events will be monitored and recorded.

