### 3.3.1 Visit 2 (Week -2)

- Review of concomitant medication;
- Measurement of weight;
- Urine pregnancy test (women of childbearing potential/WCBP only) prior to dosing;

- Dispense 1 bottle of placebo with instructions for administration. Subjects will receive placebo 8 mg (1 x 8 mg capsule) administered twice daily, once in the morning approximately 30 to 45 minutes prior to breakfast and no later than 10AM, and once at night between 8 PM to Midnight and no sooner than 1 hour after dinner;
- Measurement of vital signs (SBP/DBP, heart rate and oral temperature);
- Measurement of fasting blood glucose and fasting insulin for HOMA estimates;
- Diaries will be dispensed for each week for subjects to self-monitor fasting morning blood glucose;
- Self-monitored fasting morning blood glucose (finger-stick) recorded in the patient diaries 3 days weekly in the morning;
- AEs/SAEs assessment;
- Subjects will be administered morning placebo medication in clinic followed by a small snack after 30 to 45 minutes;
- Remind subjects to arrive fasting for Visit 3 in 2 weeks.

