## 5 STUDY TREATMENT (IMP)

### 5.1 Description of Investigational Drug

Active:

Code name: ORMD-0801

Dosage form: 1 soft gelatin capsule administered BID (1 capsule in the morning and 1 capsule at night)

Strength: 8 mg insulin per capsule

Description: API (recombinant human insulin USP), in Oramed's proprietary formulation [SBTI, disodium EDTA, fish oil, aerosil, and TWEEN 80] in capsules.

Placebo control:

Fish oil in capsules, identical in appearance to ORMD-0801, administered BID (one capsule in the morning, prior to breakfast and one capsule at night), daily.

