## 5.3 IMP Administration

### 5.3.1 Week 0 to Week 12 (Visit 3 to Visit 8)

The treatment regimen will consist of a soft gelatin capsule containing 8 mg insulin, and 75 mg SBTI. Sufficient quantity of medication will be dispensed to last until the next nominal clinic visit. ORMD-0801 morning treatment will be administered in clinic during Visits 3, 6 and 7. Subjects will receive either 8 mg ORMD-0801, 1 capsule twice a day (once in the morning approximately 30 to 45 minutes prior to breakfast and no later than 10 AM, and once at night between 8 PM to Midnight and no sooner than 1 hour after dinner) or matching placebo.

At Visits 2 (Placebo Run-in), 3, 6, and 7 blood samples and weights will be taken prior to morning dosing in clinic, followed by a small snack after 30 to 45 minutes.

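### Fish oil is listed for both the active and placebo capsules, yet soy is the only allergy that bars entry, so no written criterion excludes a patient with known allergy to fish oil or another capsule component

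*Combined protocol and SAP*

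**What the plan says.** **Eligibility.** Item 24, the last in Section 4.2 and repeated in the synopsis, reads "Known allergy to soy". It is the only criterion that concerns allergy.

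**Active capsule.** Section 5.1 lists recombinant human insulin with "SBTI, disodium EDTA, fish oil, aerosil, and TWEEN 80] in capsules". The Introduction, under Proposed Mechanism, also names a soybean-derived component and fish oil: "3) soybean trypsin (SBTI), and (4) omega 3-rich fish oil, in a coated capsule". Section 5.3.1 gives the soybean component as 75 mg per capsule.

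**Placebo.** Section 5.1 describes it as "Fish oil in capsules, identical in appearance to ORMD-0801, administered BID". No other placebo composition appears in the protocol.

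**Run-in.** Section 3.1 states "All subjects will receive the morning treatment (Run-in Placebo) in clinic" at Visit 2. Section 3.3.1 adds "Dispense 1 bottle of placebo with instructions for administration" and schedules one capsule twice daily for the two weeks before Visit 3.

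**The concern.** The criteria treat allergy to one capsule ingredient as a reason not to enrol. The protocol does not say why soy was chosen, but the soybean trypsin component is the evident explanation. That component is listed for the active capsule only. Fish oil is listed for both capsules, and the criteria do not address allergy to it. They are equally silent on the remaining listed ingredients.

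What is at stake is the safety of the individual participant. A candidate whose screening history records a fish-oil allergy meets no written exclusion and could start capsules at Visit 2, before any randomized treatment. Safety is the trial's primary objective, so the entry rules should match the contents of the capsules.

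**Working it through.** No power or sample-size figure is involved, and the plan states no figure to reproduce. The check sets composition against eligibility and then counts scheduled exposure.

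**1. Who receives which component**

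| Component | Active capsule (Section 5.1) | Placebo capsule (Section 5.1) | Allergy criterion |
|---|---|---|---|
| Soybean trypsin component (SBTI) | listed | not listed | yes, item 24 |
| Fish oil | listed | listed | none |
| Insulin, disodium EDTA, aerosil, TWEEN 80 | listed | not listed | none |
| Soft gelatin shell | listed | only capsules stated | none |

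**2. Search of the entry criteria**

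- There are 12 inclusion + 24 exclusion = 36 criteria. One concerns allergy (soy). None concerns allergy to fish, fish oil or another component.
- Exclusion 6, the nearest general medical exclusion, lists organ systems and disease groups. Allergic or immunologic disease is not among them.
- Inclusion 11 mentions fish oil only as a prior treatment that must have been stopped.
- No exclusion allows the investigator to decline a patient for an unlisted risk. The clause on unacceptable risk in Section 4.3 (item 8) is a reason to end participation, not an entry criterion.
- Section 7.6.1, on potential adverse events of the product, does not mention allergic reactions.

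**3. Scheduled exposure per completer**

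- Run-in: 14 days × 2 capsules = 28.
- Treatment: 84 days × 2 capsules = 168.
- Fish-oil capsules in either arm: 28 + 168 = 196, taking the run-in placebo to be the one in Section 5.1.
- Capsules with the soybean component: 168 in the active arm, 0 in the placebo arm.
- Under 2:1 allocation of about 36 subjects: 36 × 2/3 = 24 active and 36 × 1/3 = 12 placebo.

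The one allergy criterion therefore covers an ingredient listed for about two thirds of randomized subjects and leaves out the ingredient listed for all of them. These counts use nominal days; the ±4-day visit windows change them slightly and do not affect the point.

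**The case against.** The strongest reply is that the documents do not show how large the risk is. They do not give the source, refinement or residual protein of the oil, so the step from fish oil in the capsule to danger for an allergic patient cannot be sized from the text. Nor do they give the number of candidates affected. Both points stand, and no estimate of either is offered here.

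A reader might infer that the primary safety comparison is compromised. The documents do not support that:

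- A reaction to an ingredient shared by both arms is something a concurrent placebo helps to reveal.
- Section 8.2.1 plans descriptive reporting of adverse events, with no inferential comparison between arms.
- Under the same section, run-in events are classed as pretreatment and listed apart from treatment-emergent events.
- The first placebo capsule is taken in clinic at Visit 2, two weeks before the Visit 3 dose. Section 4.3 allows replacement of subjects who withdraw before treatment. If that means the Visit 3 treatment, a reaction in the run-in need not cost a randomized subject.

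A reader might also infer that sites would in fact enrol and dose such a patient. The text supports only that no written criterion forbids it. A complete medical history is taken at screening (Sections 3.2.1 and 6.2), possible hazards are explained at consent (Section 6.1), and Section 4.3 allows later withdrawal. The consent form and the investigator's brochure were not available for this review and may carry hypersensitivity warnings. These are partial safeguards, and none of them is an entry criterion.

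Three links are inferences: that item 24 reflects the soybean component, that the run-in capsule is the Section 5.1 placebo, and that the placebo shell is also soft gelatin. All are plausible and none is stated. The gap does not depend on the first or the third. Without the second, fish oil would still be listed for both randomized arms.

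It can also be said that no two passages contradict each other. That is so: the mismatch is between the scope of an entry rule and the list of ingredients to which such a rule would apply.

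**Conclusion.** The gap is real and small. Fish oil is listed for both capsules, soy is the only allergy in the entry criteria, and nothing in Section 4.1 or 4.2 bars a patient with known allergy to fish oil or another component. On the written schedule a completer in either arm takes 196 capsules with fish oil, assuming the run-in placebo has the Section 5.1 composition.

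The probability that it matters for any one participant is taken to be low, and neither the probability nor the severity can be quantified from the documents. The point is an avoidable participant-safety gap. It does not weaken the descriptive safety analysis or the liver-fat analysis. It merits correction because the entry rule can be brought into line with the protocol's own ingredient list at almost no cost.

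**What to change.** Reconcile the eligibility list with the capsule composition. Extend exclusion 24, in both Section 4.2 and the synopsis, to known allergy or hypersensitivity to any component of the active or placebo capsule listed in Section 5.1. Check it from the medical history already taken at Visit 1. In the same edit, state in Section 5.1 whether the run-in placebo and the placebo shell have the composition given there. If the sponsor has grounds to regard the oil or another ingredient as free of allergic risk, the protocol can say so and narrow the criterion accordingly.

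The cost is one line in two places and one history question. The downside is an occasional extra screen failure. Sample size, randomization and analysis are unaffected.
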